### **Coumarin-based Anticoagulants**

Lomitapide increases the plasma concentrations of warfarin and increases INR. Increases in the dose of lomitapide may lead to supratherapeutic anticoagulation, and decreases in the dose may lead to subtherapeutic anticoagulation. Patients taking warfarin should undergo regular monitoring of the INR, especially after any changes in the dose of lomitapide. The dose of warfarin should be adjusted as clinically indicated.

### **Hepatotoxic Agents**

Caution should be exercised when lomitapide is used with other medicinal products known to have potential for hepatotoxicity, such as isotretinoin, amiodarone, acetaminophen (>4 g/day for ≥3 days/week), methotrexate, tetracyclines, and tamoxifen. The effect of concomitant administration of lomitapide with other hepatotoxic medicine is unknown. More frequent monitoring of liver function tests may be warranted.

## **7.4 Patient Discontinuation Criteria**

Patients and/or their parents/legal guardians will have the right to withdraw from the study at any time for any reason without prejudice to their future medical care. A patient may be withdrawn from the study at any time at either the investigator's, sponsor's, or DSMB's discretion.

A patient **must** be discontinued from the study for any of the following reasons:

- The patient matches the criteria referred to as “Hy’s law case” according to the EASL Clinical Practice Guidelines on Drug-induced Liver Injury (EASL 2019) and the FDA Guidance for Industry Drug-Induced Liver Injury Premarketing Clinical Evaluation (FDA 2009). Any Hy’s law case or comparable signs of liver toxicity, irrespective of origin, must lead to permanent treatment discontinuation of the individual patient (no re-challenge allowed).
- The patient and/or his/her parent/legal guardian withdraws assent/consent.
- Pregnancy as evidenced by a positive pregnancy test.

If a patient becomes pregnant during the study, during the follow-up, or 30 days within the last application of study medication, the sponsor will have to be informed within 24 hours. The investigator will be asked to complete a pregnancy report provided by the sponsor. He/she will be asked to obtain data on the course of the pregnancy, including perinatal and neonatal outcome (see Section 11.5.4 *Other Reportable Information*).

- Any AE which, in the opinion of the investigator, places the patient at unacceptable risk, including intolerable AE(s) after attempted dose reduction (see Section 7.3.2 *Dose Modification, Interruption, or Discontinuation for Adverse Events*).

The investigator will be able to withdraw patients from the study for the following reasons:

- Hepatobiliary criteria for discontinuation
- Hepatobiliary AE CTCAE Grade 4 (see Appendix 3 *Common Terminology Criteria for Adverse Events, Hepatobiliary Disorders*), regardless of relationship to study drug
- Biochemical hepatobiliary guideline Level 4 Hepatotoxicity or Level 3 Hepatotoxicity that persists despite interruption of study drug
- Histopathological diagnosis of Type 3 or Type 4 NASH
- Patient is noncompliant with the study procedures or medications in the opinion of the investigator
- Progression of a medical condition, which in the opinion of the investigator should preclude further participation of the patient in the study (e.g., excessive weight loss)
- Administration of non-permitted concomitant medication(s), substances, or foods
- Investigators’ decision that a change of therapy is in the patients’ best interest
- Occurrence of an AE (including abnormal laboratory findings), which makes discontinuation desirable or necessary in the investigators’ and/or the patients’ opinion

If a patient discontinues the study or the follow-up prematurely due to an AE/SAE, he/she will be followed up until the resolution or stabilisation of the AE/SAE.

If a patient discontinues the study prematurely, the EoT visit assessments should be made (see Section 9.7 *End of Treatment Visit*).

All data collected before premature discontinuation of the study will be used for analysis. Patients who drop out will not be replaced unless the assumptions for drop-out have been exceeded.

## 7.5 Overdose

There is no specific treatment in the event of overdose. In the event of overdose, the patient should be treated symptomatically and supportive measures instituted as required. Liver function tests should be monitored. Haemodialysis is unlikely to be beneficial given that

lomitapide is highly protein-bound. Please refer to the SPC, Section 4.9 (included in the Lojuxta® SPC in lieu of an IB; see Section 18.1 *Source Documents*) for further details.

## 7.6 Concomitant Medication

All medications that the patient is taking will be recorded in the eCRF. For each concomitant medication, the name of the medication, start and stop date, dose, indication, frequency of dosing and route of administration will be recorded. During the study, only changes of information from the previous visit at the time points indicated in Section 1.2 *Flow Chart of Study and Follow-up* will be recorded.

### 7.6.1 Concomitant Lipid-lowering Treatment

Patients will be required to remain on their concomitant LLT (including LA, when applicable) established during the 6-week Run-in Period during the Efficacy Phase of the study through Week 24±3 days. Patients with HoFH are expected to be following different treatment regimens that usually include a statin together with additional LLT such as fibrates, bile acid sequestrant, and ezetimibe, as well as LA.

Each patient's individual therapeutic regimen should not be changed during the first 24 weeks±3 days of lomitapide treatment (Efficacy Phase). After Week 24±3 days, adjustments to background LLT (including LA, when applicable) may be made as necessary for optimal standard of care.

LA treatment causes a sharp drop in LDL-C, followed by a rebound phase. Therefore, in patients undergoing LA, it is important that lipid parameters are evaluated at a time that is as close as possible to and before the scheduled LA treatment. Once established, this time point for lipid profile blood draws should always be maintained, relative to the previous LA visit, so that lipid profiles are always performed at the same point on the LDL-C rebound curve.

During the Run-in Period a stable frequency regimen (i.e., LA every X number of days) will be established. This frequency of LA needs to be maintained during the Efficacy Phase (through Week 24±3 days). The frequency of LA is usually personalised to meet the patient's needs and the centre's capacity. Therefore, windows are provided in Section 1.2 *Flow Chart of Study and Follow-up* for each visit to allow flexibility when patients can be seen. If a patient is unable to come for an LA per his/her usual regimen, LA should be rescheduled as soon as possible. If LA was missed at a time a study visit was scheduled, then blood for lipid profile should be drawn before the LA treatment and as close as possible to the LA regimen established during the Run-in Period or as revised if during the Safety Phase.

However, for Visits 4 through 21 (i.e., during the Efficacy and Safety Phase) fasting lipids must be drawn just prior to the LA and LA must occur ±3 days from the regimen established during the Run-in Period.

### 7.6.2 Permitted Concomitant Medication

The following medication will be permitted during study and follow-up:

- Lipid-lowering medicinal products including statins, fibrates, bile acid sequestrants, and PCSK9 inhibitors

Please note: Patients who receive atorvastatin, should separate the dose of the medicinal products by 12 hours, e.g., by taking atorvastatin in the morning and lomitapide in the evening (see Section 7.3.3. *Dose Modification for Concomitant Medication*). Patients who receive bile acid sequestrants, should separate the dose of the medicinal products by 4 hours. Concomitant administration of >40 mg simvastatin is not permitted (see Section 7.6.3 *Non-permitted Concomitant Medication, Food or Substances*).

- Oestrogen-based oral contraceptives

Please note: Postmenarchal female adolescent patients taking oestrogen-based oral contraceptives should be advised that diarrhoea and/or vomiting may reduce hormone absorption. In case of protracted or severe diarrhoea and/or vomiting lasting more than 2 days, the investigator should advise according to national practice, which additional contraceptive measures (such as sexual abstinence, barrier methods) should be used for 7 days after resolution of symptoms.

- Supportive therapy upon the investigators' discretion.

The following medication will be permitted during the Safety Phase of the study:

- If a weak CYP 3A4 inhibitor, e.g., aminoglutethimide, naftillin, non-nucleoside reverse transcriptase inhibitors, phenobarbital, rifampicin, carbamazepine, pioglitazone, glucocorticoids, modafinil and phenytoin inhibitor is required during the Safety Phase, the dose of lomitapide should be reduced as described in Section 7.3.3 *Dose Modification for Concomitant Medication*.

Please note: Patients who receive weak CYP 3A4 inhibitors, should separate the dose of the medicinal products by 12 hours.

If atorvastatin is given concomitantly, it should be administered in the morning to separate it from lomitapide dosing by 12 hours. In case it is not possible to administer atorvastatin and lomitapide 12 hours apart, the lomitapide dose should be reduced by half (see Section 7.3.3 *Dose Modification for Concomitant Medication*).

### **7.6.3 Non-permitted Concomitant Medication, Food or Substances**

#### **Non-permitted Concomitant Medication**

The following medication will not be permitted during the study:

- Contraindications for the use of lomitapide according to section 4.3 of the SPC (included in the Lojuxta® SPC in lieu of an IB; see Section 18.1 *Source Documents*), such as
  - Concomitant administration of >40 mg simvastatin.
  - Concomitant use of strong or moderate CYP 3A4 inhibitors, e.g., antifungal azoles such as itraconazole, fluconazole, ketoconazole, voriconazole, posaconazole; macrolide antibiotics such as erythromycin or clarithromycin; ketolide antibiotics such as telithromycin; HIV protease inhibitors; the calcium channel blockers diltiazem and verapamil, and the anti-arrhythmic dronedarone.

The following medication will not be permitted during the Efficacy Phase of the study:

- Weak CYP 3A4 inhibitors, e.g., aminoglutethimide, naftillin, non-nucleoside reverse transcriptase inhibitors, phenobarbital, rifampicin, carbamazepine, pioglitazone, glucocorticoids, modafinil and phenytoin. If a weak CYP 3A4 inhibitor is required during the Safety Phase, the dose of lomitapide should be reduced as described in Section 7.3.3 *Dose Modification for Concomitant Medication*.

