During the 80-week Safety Phase, the lomitapide dose can be reduced from the MTD due to tolerability or safety issues, and the patient can be re-challenged with a higher dose of lomitapide once these issues resolve (after a minimum period of 4 weeks following dose reduction), but the dose during the Safety Phase cannot exceed the MTD established during the Efficacy Phase unless eligibility for exceptional dose escalation described above is met.

Please refer to Section 7.3.2 *Dose Modification and Interruption for Adverse Events* for further details regarding dose reductions due to AEs and to Section 7.3.3 *Dose Modification for Concomitant Medication* for detailed information about dose reductions depending on concomitant medication.

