#### **7.3.3 Dose Modification for Concomitant Medication**

##### **Weak Cytochrome P450 (CYP) 3A4 Inhibitors**

Medicinal products that induce CYP 3A4 would be expected to increase the rate and extent of metabolism of lomitapide. CYP 3A4 inducers exert their effect in a time-dependent manner, and may take at least 2 weeks to reach maximal effect after introduction. Conversely, on discontinuation, CYP 3A4 induction may take at least 2 weeks to decline.

Co-administration of a CYP 3A4 inducer is expected to reduce the effect of lomitapide. Any impact on efficacy is likely to be variable. When co-administering CYP 3A4 inducers (i.e., aminoglutethimide, naftacin, non-nucleoside reverse transcriptase inhibitors, phenobarbital, rifampicin, carbamazepine, pioglitazone, glucocorticoids, modafinil and phenytoin) with lomitapide, the possibility of a drug-drug interaction affecting efficacy should be considered.

Strong or moderate cytochrome CYP 3A4 inhibitors are not permitted during the study as described in Section 7.6.3 Non-Permitted Concomitant Medication, Food or Substances.

Weak cytochrome CYP 3A4 inhibitors are only permitted during the Safety Phase of the study, but lomitapide should be administered 12 hours apart. If atorvastatin is given concomitantly, it should be administered in the morning to separate it from lomitapide dosing by 12 hours. In case it is not possible to administer atorvastatin and lomitapide 12 hours apart, the lomitapide

dose should be reduced by half, as the lomitapide dose can be reduced from the MTD due to tolerability or safety issues during the 80-week Safety Phase. After a minimum period of 4 weeks following dose reduction the patient can be re-challenged with a higher dose of lomitapide once these issues resolve (i.e., if atorvastatin can be administered 12 hours apart or if atorvastatin is discontinued), but the dose during the Safety Phase cannot exceed the MTD established during the Efficacy Phase unless eligibility for exceptional dose escalation is met (described in Section 7.3.1 *Dose Escalation, Dose Reduction and Re-challenge*).

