#### **Non-permitted Concomitant Food or Substances**

The use of the following food or substances should be avoided with lomitapide:

- Alcohol: Alcohol may increase levels of hepatic fat and induce or exacerbate liver injury.
- Grapefruit juice: Grapefruit juice is a moderate inhibitor of CYP 3A4 and is expected to substantially increase exposure to lomitapide.
- Peppermint oil or Seville oranges.
- St. John's Wort (i.e., *Hypericum perforatum*).

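### Section 7.3.3 calls ten drugs CYP 3A4 inducers, while the synopsis and Sections 7.6.2 and 7.6.3 call them weak inhibitors and require a Safety Phase lomitapide cut that 7.3.3 does not give for them

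*Protocol*

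**What the plan says.** **Labelled as weak inhibitors.** Section 7.6.3 names, among medication barred in the Efficacy Phase, "Weak CYP 3A4 inhibitors, e.g., aminoglutethimide, naftillin, non-nucleoside reverse transcriptase inhibitors, phenobarbital, rifampicin, carbamazepine, pioglitazone, glucocorticoids, modafinil and phenytoin". It adds that if a weak inhibitor becomes necessary in the Safety Phase, lomitapide is to be reduced, and it points to Section 7.3.3 for how. Section 7.6.2 gives the same examples and the same pointer, and also asks for 12-hour separation. The synopsis carries the list twice under concomitant treatment, each time with both a reduction and 12-hour separation.

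**Labelled as inducers.** Section 7.3.3, under a sub-heading about weak inhibitors, says "When co-administering CYP 3A4 inducers (i.e., aminoglutethimide, naftacin, non-nucleoside reverse transcriptase inhibitors, phenobarbital, rifampicin" and continues through the same remaining names. It states: "Co-administration of a CYP 3A4 inducer is expected to reduce the effect of lomitapide". It also notes that "on discontinuation, CYP 3A4 induction may take at least 2 weeks to decline". For these drugs it asks only that a possible interaction affecting efficacy be kept in mind.

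**Dose instructions in Section 7.3.3.** For weak inhibitors: "Weak cytochrome CYP 3A4 inhibitors are only permitted during the Safety Phase of the study, but lomitapide should be administered 12 hours apart". The only reduction in the section concerns atorvastatin when the two drugs cannot be spaced 12 hours apart; then the lomitapide "dose should be reduced by half, as the lomitapide dose can be reduced from the MTD due to tolerability or safety issues".

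**Section 7.3.1.** It sends the reader to Section 7.3.3 "for detailed information about dose reductions depending on concomitant medication". It also has a general rule, repeated in the synopsis, for any reduction that is needed: go down to the last tolerated dose or to an intermediate one.

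**The concern.** The protocol itself treats the two mechanisms as opposite. Induction speeds up lomitapide metabolism and weakens its effect (Section 7.3.3). Inhibition raises exposure; Section 7.6.3 says of one example that "Grapefruit juice is a moderate inhibitor of CYP 3A4 and is expected to substantially increase exposure to lomitapide". One drug list therefore cannot serve both labels under one dosing rule.

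Two things are at stake. First, a site that follows Section 7.6.2 or 7.6.3 lowers lomitapide when one of the ten is added, although Section 7.3.3 says the effect is already expected to fall. Second, a site that follows the pointer to Section 7.3.3 finds no reduction for these agents, so sites can comply with one section while departing from another. Both bear on a child's benefit and safety in the Safety Phase, and on the lipid results collected after Week 24.

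**Working it through.** No formula applies. The check is a side-by-side reading of the lists and the instructions.

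**1. Are the lists the same?** Section 7.3.3 has ten entries. Each of the four weak-inhibitor lists (two in the synopsis, one each in Sections 7.6.2 and 7.6.3) also has ten, in the same order. Nine are spelt identically; the second differs by a spelling variant, which carries no weight. Result: 10 of 10 entries carry both labels.

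**2. What does each label imply for the dose?** If an entry is an inducer, Section 7.3.3 expects less lomitapide effect, so a cut pushes the same way as the interaction. Spacing the doses by 12 hours does not address induction that, by the same section, may need at least 2 weeks to wear off. If an entry is an inhibitor, exposure rises and a cut is at least in the right direction.

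**3. Where does the pointer lead?** Reductions in Section 7.3.3: one in total (atorvastatin, halved, only if separation fails). Reductions there that apply to the ten: none. Because Section 7.6.2 still requires a reduction, what remains is the general step-down in Section 7.3.1.

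**4. What is the rule for weak inhibitors in general, whatever the examples?**

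| Place | Separate by 12 hours | Reduce lomitapide |
|---|---|---|
| Section 7.3.3 | yes | not stated (atorvastatin exception only) |
| Section 2.6.3 (weak inhibitors other than atorvastatin, stable maintenance dose) | yes | not stated |
| Section 2.6.2 | either separate or modify the dose | either separate or modify the dose |
| Synopsis, dosage (CYP 3A4 inhibitor added in Safety Phase) | not stated | yes |
| Synopsis, permitted medication | yes | yes |
| Synopsis, non-permitted medication | yes | yes |
| Section 7.6.2 | yes | yes, as in 7.3.3 |
| Section 7.6.3 | not stated | yes, as in 7.3.3 |

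The section named as the source of the rule gives separation only; the sections that cite it require a reduction. The cross-reference is incomplete and the instructions do not agree.

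**5. When could the rule apply?** Week 24 to Week 104 is 80 of 104 treatment weeks (80/104 = 77%). Scheduled on-treatment lipid visits after Baseline: 6 (Weeks 4 to 24) + 8 (Weeks 28 to 56) + 3 (Weeks 68, 80, 92) + 1 (Week 104) = 18, of which 8 + 3 + 1 = 12 fall after Week 24. This is the window in which the rule could bite, not the size of any effect; the protocol does not say how many patients would take one of the ten.

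**The case against.** The double labelling itself is hard to contest. The case on the other side is about how far it reaches, and much of it stands.

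- *The size of the cut.* A reader might infer that the dose after a required cut is wholly undefined. It is not: the step-down in Section 7.3.1 covers any required reduction. What is missing is an agent-specific size, and the pointer to Section 7.3.3 remains defective.
- *Opposed rules for weak inhibitors.* A reader might infer that the sections forbid what others require. Sections 7.3.3 and 2.6.3 are silent on a general reduction rather than excluding one, Section 2.6.3 is limited to patients on a stable maintenance dose, and three of the places that require a reduction also require separation. Synopsis and body text largely repeat each other, so counting places for and against adds little.
- *Time scales.* A reader might set 12 hours against 2 weeks as a ratio. These are a dosing interval and a wash-out of induction, so the ratio has no meaning, and the 2-week figure is itself hedged. Only the qualitative point stands.
- *Which label is right.* A reader might infer that all ten are inducers and the reduction is simply wrong. The protocol gives two labels and nothing that decides between them, drug by drug.
- *Existing safeguards.* Section 7.3.3 already asks that a loss of efficacy be considered. Lipids are drawn every 4 weeks to Week 56 and every 12 weeks thereafter, re-challenge is possible after at least 4 weeks once the cause resolves, and background lipid-lowering therapy may be adjusted after Week 24. These would reveal a loss of effect and allow some correction. They do not repair the text.

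**Conclusion.** The point holds as an internal contradiction that should be fixed. Ten of ten entries are inducers in Section 7.3.3 and weak inhibitors in the synopsis and Sections 7.6.2 and 7.6.3, and the Safety Phase reduction attributed to Section 7.3.3 is not there for them. This is a dosing rule that is wrong as written, not detail left to another document.

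That the cut would worsen a loss of effect is conditional on Section 7.3.3's label being the right one. The effect on the trial's conclusions is modest: it touches only Safety Phase dosing and the lipid endpoints after Week 24, which are analysed without multiplicity adjustment while background therapy may change. A reader might infer that the primary result is at risk. The documents do not support that: the ten named agents are barred throughout the Efficacy Phase, so the Week 24 analysis and the sample size are untouched. Confidence in the conflict is high; its practical size is unknown because use of these drugs is not given.

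**What to change.** 1. Have the sponsor's clinical pharmacology team confirm the class of each of the ten entries.
2. Remove confirmed inducers from the weak-inhibitor examples in the synopsis (both places) and in Sections 7.6.2 and 7.6.3. List them once, as inducers, with their own rule: no lomitapide reduction on account of induction, monitoring for loss of effect, and an explicit ban in the Efficacy Phase so that the present protection is not lost when they leave the other list.
3. State one rule for true weak inhibitors in Section 7.3.3: separate, reduce or both, with the size of any reduction or a reference to the Section 7.3.1 step-down.
4. Align the synopsis (dosage, permitted and non-permitted medication) and Sections 2.6.2, 2.6.3, 7.6.2 and 7.6.3 to that rule, so that the pointers to Section 7.3.3 reach a stated instruction.

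The cost is amendment text, a pharmacology check of ten entries and a notice to sites. It needs no extra patients, visits or procedures, and no change to the primary analysis.

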#### **Non-permitted Concomitant Food or Substances**

The use of the following food or substances should be avoided with lomitapide:

- Alcohol: Alcohol may increase levels of hepatic fat and induce or exacerbate liver injury.
- Grapefruit juice: Grapefruit juice is a moderate inhibitor of CYP 3A4 and is expected to substantially increase exposure to lomitapide.
- Peppermint oil or Seville oranges.
- St. John's Wort (i.e., *Hypericum perforatum*).

## 8 ASSESSMENTS

Please refer to Section 1.2 *Flow-Chart of Study and Follow-up* for a tabular overview of assessments by visit.

